6.2 Initial procedures

On Days 3, 5, and 7 vital signs and an ECG will be recorded at 5 hours post morning dose (time window 3.5 – 6 hours) with QTc interval assessed. If the QTc interval is > 500 msec or shows an increase of > 60 msec from baseline, the study medication must be stopped immediately.

In addition to prolongation of the QTc, careful observation is required to detect other ADRs and DDIs. Because CardiolRx™, inhibits a number of CYP and uridine diphosphate glucuronosyl transferase (UGT) enzymes, the metabolism of other drugs may be impaired, thereby resulting in increased concomitant drug blood levels; therefore, new symptoms may represent toxicity from a concomitant medication that had previously been well tolerated. For more detailed discussion, see section 6.3 of the IB.

In addition, to aid investigators in screening concomitant medications for risk of DDIs, a table of medications that serve as substrate for certain enzyme isoforms inhibited by CardiolRx™ has been prepared (Appendix 17.10).

Frozen samples will be retained for central analysis of CBD levels, hs-troponin, NT-proBNP, D-dimer as well as inflammatory markers (hs-CRP, ferritin, TNF-alpha, IL-1 beta, IL-6, IL-10) and additional parameters of interest every two days until Day 7 as well as on Day 28.

If the patient is discharged before Day 7, the assessments up to Day 7 will be carried out as out-patient or home visits.

After Day 7, all remaining scheduled assessments will be carried out during out-patient visits.

6.3 Follow-up procedures

After Day 7, routine assessments will be carried out on a weekly basis until Day 28.

On Day 28 the assessments include the following: Physical examination (including vital signs), ECG (recorded 5 hours post morning dose [time window 3.5 – 6 hours] for assessment of QTc interval), echocardiogram to measure LVEF, chest X-ray and local and central laboratory assessments, including CBC, AST/ALT, alkaline phosphatase, bilirubin, creatinine/eGFR, INR, lymphocyte count and LDH. In addition, a C-SSRS will be completed and the patient will be asked to answer a PICQ. A subset of patients at selected sites will also undergo a CMR assessment, either on Day 28 or 45.

Further follow-up visits are scheduled for Day 45 and Day 60 post randomization. These include a clinical assessment, including vital signs as well as the completion of the PICQ (at Day 60 only).

Changes in concomitant medications, AEs and SAEs will be recorded during all study visits after consent has been obtained.

6.4 Randomization Procedure

Randomization will be accomplished by means of a web-based randomization system and will be stratified by center.

PROPRIETARY AND CONFIDENTIAL

The randomization sequence will be generated by random computerized sequence in blocks of 4.

6.5 Study Medication

6.5.1 Active Study Medication

CardiolRx™ (cannabidiol) oil contains cannabidiol at a concentration of 100 mg/ml. Inactive ingredients include medium-chain triglyceride (MCT) oil and Vitamin E:

Component	Function	Strength	
		10% w/v	
		Quantity per ml	%
-(-) Cannabidiol	Active pharmaceutical ingredient (API)	100 mg/ml	10% w/v
Vitamin E	Anti-oxidant	10 mg/ml	1.0% w/v
Medium Chain Triglycerides	Solvent	0.890 ml	89.0% w/v
Total		1 ml	100.0%

6.5.2 Placebo

The placebo contains all of the inactive ingredients and none of the active ones:

Component	Function	Strength (label claim)	
		Placebo	
		Quantity per mL	%
Vitamin E	Anti-oxidant	10 mg/ml	1.0 % w/v
Medium Chain Triglycerides	Solvent	q.s. to 1 ml	~99%
Total		1 ml	100%

6.6 Blinding

Placebo will match active study drug in odor, taste, color and appearance to assure proper blinding.

6.7 Premature Interruption or Withdrawal from Study Treatment

Prior to suspending the study treatment, permanently or temporarily, if possible, the investigator needs to contact the Medical Monitor to discuss the reason(s) for suspension.

6.7.1 Permanent Suspension of Study Treatment

The investigator may permanently suspend the treatment in the following cases:

- If the patient's QTc interval is > 500 msec or an increase from baseline of > 60 msec is observed (please refer to section 9.2.3 for BBB correction);
- A DDI is identified with a concomitant medication that is medically required and cannot be resolved without the discontinuation of the study medication;

- If, in the view of the investigator, the patient experiences a severe allergic reaction that cannot be explained by the administration of any other medication;
- Development of liver function abnormality, as described in section 9.2.14.3.
- Development of an AE or any medical condition, which, in the opinion of the investigator, necessitates permanent suspension of study treatment;
- Withdrawal of consent.
- If the blind is broken (only allowed in emergency situations to determine appropriate patient care)

Patients have the right to discontinue study treatment for any reason. However, unless they withdraw consent and are no longer willing to participate, they should be followed for the remainder of the trial and all (S)AEs should be reported, regardless of whether or not the event is of CV origin or occurs under the care of another physician or institution.

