electrocardiogram (ECG) including QTc interval assessment, echocardiogram to measure left-ventricular ejection fraction (LVEF), chest X-ray, local laboratory (including complete blood count [CBC], Alanine aminotransferase [ALT]/ Aspartate aminotransferase [AST], alkaline phosphatase, bilirubin, creatinine/ estimated Glomerular filtration rate [eGFR], international normalized ratio [INR], serum pregnancy test [in women with child-bearing potential only], glucose, total cholesterol, lymphocyte count and lactate dehydrogenase [LDH]. A Columbia-Suicide severity rating scale (C-SSRS will also be completed). Frozen samples will be retained for central analysis of CardiolRx™ levels, high sensitivity troponin (hs-troponin), N-terminal pro b-type natriuretic peptide (NT-proBNP), D-dimer as well as inflammatory markers (high sensitivity C-reactive protein [hs-CRP], ferritin, tumor necrosis factor [TNF]-alpha, interleukin [IL]-1 beta, IL-6, IL-10).

If all eligibility criteria are met, the patient will be randomized to either CardiolRx™ or placebo. Randomization must be no later than 96 hours after hospital admission. Patients awaiting planned admission to hospital in an emergency room for less than 96 hours can be screened and enrolled into the trial.

Study treatment will be initiated in the evening of Day 1 after all baseline assessments have been completed and the patient is randomized.

Oral administration is as follows:

Study Day	a.m. dose [mg/kg of body weight] CardiolRx™ or placebo	p.m. dose [mg/kg of body weight] CardiolRx™ or placebo
1	N/A	2.5
2	2.5	2.5
3	2.5	5
4	5	5
5	5	7.5
6 - 28	7.5	7.5

Study medication must be taken with food.

If the next higher dose is not tolerated, the dose will be reduced to the previous tolerated dose. The highest tolerated dose will be administered until Day 28.

On Days 3, 5, and 7, an ECG will be recorded 5 hours post morning dose (time window 3.5 – 6 hours) with QTc intervals measured. If the QTc interval is >500 msec or an increase of > 60 msec from baseline is observed, the study medication must be stopped immediately.

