6.7.2 Temporary Suspension of Treatment

Temporary suspension of study treatment (up to 5 days) can occur in case of development of an (S)AE or a medical condition, which, in the opinion of the investigator, necessitates temporary interruption of study treatment, including a new finding of eGFR < 30 ml/min.

After temporary interruption of study treatment, all efforts should be made to re-institute study treatment using the last tolerated dose as soon as the clinical condition of the patient has stabilized.

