Because of this concern, an electrocardiogram (ECG) will be recorded every other day for the first 7 days of drug dosing and on Days 14, 21 and 28; the recording should be done 5 hours after the morning dose of the study drug (time window 3.5 – 6 hours). The ECG will be assessed by the Investigator at the clinical site, the QT interval measured (the QTc calculated) and recorded in the case report form (CRF), with a copy of the ECG appended. The QT interval is measured from the beginning of the QRS complex to the end of the T wave and averaged over three cardiac cycles. The average QT interval should be corrected for heart rate variability using Bazett's formula ($QT_c = QT / \sqrt{RR}$) or Fridericia's formula ($QT_c = QT / RR^{1/3}$) to create the QTc interval. Each patient should have the QTc measured using the same method on all designated days in the study. If the QTc interval increases to 500 msec or more – or increases 60 msec or more from the baseline recording on any one measurement, this will be reported as an SAE and the study medication will be discontinued.

The QT interval can be obtained from the automated measurements of the ECG recorder, unless the data quality is poor. It is the corrected value that is to be recorded in the CRF.

After 100 patients have completed the Day 28 assessment (or terminated the study earlier), the QTc data will be analyzed (unblinded) by the DSMC. If an impact on the QTc interval by the study drug has been found, the DSMC will evaluate the appropriateness of continuing the trial.

The presence of a bundle branch block represents a particular challenge in properly measuring the QTc interval. Following international recommendations, QT interval should be measured in leads showing the longest QT interval, which is usually in right precordial leads. In presence of a BBB, these leads are strongest affected by conduction delay and therefore hamper adequate measurement. A new formula for evaluation of the QT interval in patients with left bundle branch block (LBBB) was introduced in 2014:

$$QT_{mean} = QT_{BBB} - 50\% QRS_{BBB} \text{ (Bogossian et al. 2014)}$$

This formula has proved to be a reliable tool in clinical practice for QTc interval evaluation in patients with LBBB, right bundle branch block (RBBB) or bifascicular block. (Bogossian et al. 2020; Erkacic et al. 2020)

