If the QTc interval increases to 500 msec or more – or increases 60 msec or more from the baseline recording on any one measurement, this must be reported as an SAE and the study medication must be discontinued.

Other clinically relevant ECG changes also need to be reported as an AE or SAE.

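### The QTc stopping rule has two cut-offs: above 500 msec or above +60 msec in three places, but 500 or +60 msec and over in Protocol 9.2.3

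*Protocol*

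**What the plan says.** The rule appears five times in the protocol.

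- **Synopsis (Design & Methodology)**, after the Day 3, 5 and 7 ECG instructions: "If the QTc interval is >500 msec or an increase of > 60 msec from baseline is observed", study drug must be stopped at once.
- **Section 6.2**, in the same context and with the same strict limits: "the study medication must be stopped immediately".
- **Section 6.7.1**: the QTc trigger ("QTc interval is > 500 msec or an increase from baseline of > 60 msec is observed") is the first item in a list introduced by "The investigator may permanently suspend the treatment in the following cases". It refers to 9.2.3 only for the bundle branch block correction.
- **Section 9.2.3, first statement**: "If the QTc interval increases to 500 msec or more", or by 60 msec or more from baseline on any single measurement, an SAE will be reported and the drug will be discontinued.
- **Section 9.2.3, second statement**, after the bundle branch block formula: the same inclusive limits, and "this must be reported as an SAE and the study medication must be discontinued".

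The SAP summarises ECG values (9.3.6) and tabulates serious treatment-emergent events and those leading to discontinuation (9.3.8). It contains no QTc stopping rule.

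**The concern.** A stopping limit for an individual patient should give the same answer wherever a site looks it up. Here the inequality differs between sections, and only 9.2.3 attaches an SAE report. Two sites with the same boundary reading could act differently: one stops the drug and files an SAE, the other does neither. That would carry into the SAP's tables of serious events and of events leading to discontinuation. SAP 9.3.6 names no count of readings at 500 or +60 msec that would reveal it.

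Section 9.2.3 treats QTc prolongation through drug interaction as a particular concern and records a regulator's request for repeated QTc assessment, so the rule deserves one clear form.

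**Working it through.** No figure in the plan needs reproducing; the check is a comparison of the five statements.

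| Place | QTc limit (msec) | Rise limit (msec) | Action on study drug | SAE duty stated |
|---|---|---|---|---|
| Synopsis | > 500 | > 60 | must stop | no |
| 6.2 | > 500 | > 60 | must stop | no |
| 6.7.1 | > 500 | > 60 | may suspend permanently | no |
| 9.2.3, first | ≥ 500 | ≥ 60 | will be discontinued | yes |
| 9.2.3, second | ≥ 500 | ≥ 60 | must be discontinued | yes |

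**Step 1: where the limits disagree.** Every reading above a strict limit also meets the inclusive one. The rules therefore differ only when neither strict limit is exceeded and at least one value sits on its boundary:

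- QTc exactly 500 with a rise of 60 or less, or
- a rise of exactly 60 with QTc of 500 or less.

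Such a reading meets 9.2.3 and none of the other three.

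**Step 2: whether anything settles it.** The cross-reference in 6.7.1 to 9.2.3 covers only the bundle branch block correction, so it does not import the 9.2.3 limits. The SAP has no rule. The conflict stays open.

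**Step 3: the verb.** Four statements require a stop. Section 6.7.1 alone permits one.

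**Step 4: size.** The documents give no QTc mean or standard deviation (SD), so the number of patients cannot be estimated. The following only illustrates how narrow the boundary is. It counts readings, not patients, and every mean and SD is an assumption. Section 9.2.3 schedules six post-baseline ECGs (Days 3, 5, 7, 14, 21, 28), so the planned maximum is 422 × 6 = 2,532 readings. With recording in whole msec and normal distributions, expected boundary readings ≈ 2,532 × density at the boundary × 1 msec.

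- *Rise exactly 60, mean change 0, SD 20:* density = exp(−60²/(2 × 20²)) / (20 × √(2π)) = 0.0111 / 50.13 = 0.000222; × 2,532 = 0.56 readings. SD 15, 30 and 40 give 0.02, 4.56 and 8.20.
- *QTc exactly 500, mean 440, SD 25:* density = exp(−60²/(2 × 25²)) / (25 × √(2π)) = 0.0561 / 62.67 = 0.000896; × 2,532 = 2.27 readings. Mean 430 with SD 20 gives 0.11; mean 450 with SD 30 gives 8.40.

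The top of each range should not be read as likely. SD 40 implies 173 readings at or above +60 (173 / 2,532 = 6.8%), and mean 450 with SD 30 implies 125 at or above 500 (125 / 2,532 = 4.9%). Nothing in the documents supports rates that high. The counts also ignore deaths, dropouts, stops and the early termination recorded in SAP section 2.

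**The case against.** The best defence is that the rules are nested. The synopsis, 6.2 and 6.7.1 do not tell a site to continue at the boundary; they are silent there. A site that follows 9.2.3, the detailed ECG section, breaches nothing, and 6.7.1 separately lets the investigator stop for any adverse event thought to need it. Section 9.2.3 also lets sites choose Bazett or Fridericia correction, which is likely to separate sites more than one msec does. All of this stands and keeps the point small. It does not help a site working from the synopsis or 6.2, which would not learn of the inclusive limit or the SAE duty.

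Two stronger readings are tempting.

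- **That the permissive verb in 6.7.1 makes stopping optional.** The list is a general one. It also holds withdrawal of consent and liver abnormality, and 9.2.14.3 requires discontinuation for the liver criteria. A permissive heading does not cancel four explicit requirements.
- **That a site could restart drug after a qualifying QTc.** Section 6.7.2 says "Temporary suspension of study treatment (up to 5 days) can occur in case of development of an (S)AE or a medical condition" and then "all efforts should be made to re-institute study treatment using the last tolerated dose", and 9.2.3 classes the QTc event as an SAE. But QTc is named under permanent suspension and not in 6.7.2. Section 9.2.3 speaks of discontinuation. Section 6.7.2 applies where the investigator judges an interruption necessary, whereas a QTc at the limit already has its own mandatory rule. The documents largely answer the restart question.

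**Conclusion.** The cut-off conflict is real and sits in current protocol text. At exactly 500 msec or exactly +60 msec, with neither limit exceeded, 9.2.3 requires a stop and an SAE report while the synopsis, 6.2 and 6.7.1 call for no action. The permissive verb in 6.7.1 is a secondary drafting fault.

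The effect is minor. If QTc is recorded in whole msec, only single-msec boundary readings differ, and no patient number can be derived from the documents. Safety handling and the SAE and discontinuation counts are affected. A reader might infer an effect on efficacy or on the data safety and monitoring committee's QTc review; neither follows, because the efficacy analysis does not use the stopping limit and the committee reviews the QTc data themselves. As the trial ended early, the remaining value lies in reporting which limit sites applied and in any reuse of this text.

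**What to change.** Use the 9.2.3 limits in the synopsis, 6.2 and 6.7.1: QTc ≥ 500 msec, or a rise of ≥ 60 msec from baseline, on any one on-treatment ECG. In 6.7.1, take the QTc item out from under the permissive verb and word it as mandatory. In the synopsis, 6.2 and 6.7.1, refer to the SAE duty in 9.2.3.

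A specific bar on restart, or a change of the entry limit (exclusion 10 in section 5.3, QTc above 500 msec), would be a clinical choice and is not needed to remove the conflict. The sponsor should note that, with the entry limit unchanged, a patient can enter at exactly 500 msec and sit on the stopping limit from the start.

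The cost is wording in three places and a note to sites. Visits, data collection and sample size do not change. For the closed trial, one sentence in the study report on which limit was applied would suffice.

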6.7.2 Temporary Suspension of Treatment

Temporary suspension of study treatment (up to 5 days) can occur in case of development of an (S)AE or a medical condition, which, in the opinion of the investigator, necessitates temporary interruption of study treatment, including a new finding of eGFR < 30 ml/min.

After temporary interruption of study treatment, all efforts should be made to re-institute study treatment using the last tolerated dose as soon as the clinical condition of the patient has stabilized.

6.7.3 Withdrawal of Consent

Patients may decide to fully or partially withdraw their consent to participate in the study. At that point, it should be established, whether the withdrawal is related to study treatment, further assessments, or any further involvement in the study. If the withdrawal is primarily related to study treatment or specific assessments, patients should be encouraged to continue follow-up and to attend all other subsequent study assessments. Reports of AEs and SAEs should be collected until completion of the study for all withdrawals, unless the patient objects to such follow-up.

Patients who withdraw their consent to participate in the study, whether related to study treatment or not, will not be replaced. All data available will be included in the statistical analysis.

6.8 Concomitant Treatment

Patients may be on SOC treatment(s) for all current conditions, as prescribed by their treating physician, including dexamethasone, remdesivir, baricitinib plus remdesivir, monoclonal antibodies (administered prior to admission), and convalescent plasma therapy,

[figure not shown]

PROPRIETARY AND CONFIDENTIAL

with the exception of cannabinoids and strong inducers of CYP3A4 and CYP2C19 (see Appendix 17.7).

Also, because CardiolRx™ is known to inhibit the metabolism of certain other drugs, new symptoms or findings may represent toxicity from a concomitant medication that had previously been well tolerated. Please refer to section 9.2.11 and to Appendix 17.10.

7 STUDY PLAN

* Patients awaiting planned admission to hospital in an emergency room for less than 96 hours can be screened and enrolled into the trial.

8 INVESTIGATIONAL PRODUCTS, DOSE AND DURATION OF TREATMENT

8.1 *Investigational Product*

CardiolRx™ is pharmaceutically produced. It contains cannabidiol in a concentration of 100 mg/ml and is free of tetrahydrocannabinol (THC; <5 ppm).

8.2 *Administration, Dosage and Duration of Treatment*

Study drug will be administered orally (via syringe)* with food according to the following treatment schedule:

Study Day	a.m. dose [mg/kg of body weight]	p.m. dose [mg/kg of body weight]
	CardiolRx™ or placebo	CardiolRx™ or placebo
1	N/A	2.5
2	2.5	2.5
3	2.5	5
4	5	5
5	5	7.5
6 - 28	7.5	7.5

At each study visit, drug accountability will be done. New bottles of study medication will be dispensed at each study visit (Days 3, 5, 7, 14 and 21).

If the next higher dose is not tolerated, the patient should return to the last tolerated dose. The highest tolerated dose will be administered until Day 28 (4 weeks post randomization).

The maximum treatment period will be 28 days.

* If the patient requires mechanical ventilation, the study medication is administered through a naso-gastric tube.

Justification for Dosing Regimen

COVID-19 is an acute illness with, at times, rapid progression of symptoms and signs. Because of this, it seems important to increase the blood level of the investigational agent as quickly as possible to achieve the potential anti-inflammatory and anti-cytokine actions that are likely to be important in this population. However, this agent has not been administered previously to this population, so care must be taken to observe closely for

adverse drug effects or drug-drug interactions that might have significant negative consequences. A similar product containing a highly purified botanical extract of CBD has been approved for use in pediatric epilepsy to a dose up to 10 mg/kg twice daily (Devinsky et al. 2016). We have chosen to restrict the maximum dose in this COVID-19 population to 7.5 mg/kg b.i.d. because of the expected elderly and perhaps frail condition of some of the enrolled patients. Investigators are encouraged to decrease the dose if there are indications of intolerance of a given dose to the previously tolerated dose.

8.3 Study Treatment Return and Reconciliation

A detailed treatment dispensing log will be kept at each site, which will be checked at the close-out visit. After completion of the study, including final drug accountability, all unused study materials must be destroyed locally.

8.4 Supply, Packaging, Labelling and Storage

8.4.1 Supply and Packaging

The study drug will be provided in 30 ml bottles, containing a concentration of 100 mg/ml.

8.4.2 Labelling and Storage

All study medication will be labeled in both English and the local language according to the local regulations for investigational drugs.

All clinical drug supplies are to be stored in a secure, limited-access area in accordance with labeled storage conditions:

- Controlled temperature 20°C - 25°C (68°F- 77°F) or refrigerated. Excursions up to 30° C (86 °F) that are experienced in pharmacies, hospitals, and warehouses, and during shipping are allowed, provided they do not exceed 24 hours.
- The relative humidity should not exceed 65%
- The study supplies need to be protected from light (to be kept in closed cartons or boxes).

If the patient is discharged before Day 28, the patient will administer the study medication at home. If the temperature range of < 25°C cannot be achieved in the patient's home, the patient will be asked to store the study medication in the fridge.

